5.2 CONSENTING PARTICIPANTS

CASE COHORT

1. Electronic completion. It is expected that this will form the great majority of the study. From the link the patient will access a PIS on either personal computer or mobile phone using the RedCap platform and complete an electronic checkbox to confirm they have read the PIS and have had the opportunity to ask any questions before commencing the demographic questions and questionnaires.
2. Paper or phone completion - where the participant is not able to or does not wish to complete the online form then questionnaires will be made available by other means according to the specific preferences of the participant. Verbal assent will be obtained and the data will be transferred to the online platform by a member of the research team.

NESTED CASE CONTROL: CONSENTED CRF VISIT

Participants that agree to attend a research facility in person will be consented in writing ahead of any study procedures taking place using the local process for research consent.

5.3 SCREENING FOR ELIGIBILITY

Participants will be consented to take part in the nested case control study and their SCI Diabetes records will be subsequently checked for eligibility. The research nurse will assess eligibility and will take a judgement on whether the participant is eligible at that time. It may become clear at a later date that the participant is not eligible eg. has difficulty reading questionnaires or providing written answers. Work arounds will be sought where possible (eg. verbally aid to support participation). However ineligible participants may have their data removed from the study, at the CI's discretion.

Participants assigned as controls who are subsequently found to be cases will be moved to the case arm of the study and a replacement control will be sought.

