4.5 STUDY ASSESSMENTS

Case-Cohort:

Self-completed, offered online (can be offered by phone/on paper for participants who request this).

1. Demographics
2. Questionnaires (in order of priority)
 - a. Wellcome Trust COVID 19 questionnaire (Most up to date version in use at the time of the study): This is a comprehensive instrument covering physical, cognitive, and mental health domains and will also allow comparison to developing UK reference population data). Questions deemed to require additional support have been removed.
 - b. Diabetes Related Quality of Life (DQOL)

- c. Diabetes-Specific [name]-1
 - d. EQ5D
3. Option to self-nominate for nested case control study.

Nested Case Control (CRF visit):

1. Written consent
2. Questionnaires (if not done previously) or Update of symptoms score Wellcome questionnaire section 1.3
3. Blood sample (optional) for research labs (16ml total, 6ml purple top (EDTA), 6ml gold top (serum), 4ml blue top (citrate)) for non-routine bloods: inflammatory (e.g. CRP), vascular (t-PA, vWF) and cardiac (hs troponin, NT proBNP) biomarkers consistently predictive of long-term adverse outcomes.
4. Blood sample (8ml total, 3ml purple top (EDTA) and 5ml gold top (serum)) for routine clinical measures (HbA1c, LFTs, lipids, U&Es).
5. Physical measures
 - a. Incremental walking test
 - b. Grip strength
6. Waist and thigh measurement
7. Bioimpedance (optional if site does not have this equipment)
8. Pulmonary function test (optional if site does not have this equipment)

Cases will be invited to a repeat study visit 1 year (40 to 64 weeks) from the initial study visit.

SOPs (shared from other studies) will be used to standardise:

- Incremental walk test
- Grip strength test
- Blood sampling, storage and shipment
- Pulmonary function test

Clinical data: Baseline and follow up data from SCI-Diabetes including glucose control and blood pressure.

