5 PARTICIPANT SELECTION AND ENROLMENT

5.1 IDENTIFYING PARTICIPANTS

Case Cohort: To allow as wide participation as possible, study instruments (questionnaires) will by default be offered remotely using an online implied consent and completion. For this

reason, we will include only contact details (e mail and or telephone) and limited, broad demographics (age in 5 year categories, ethnicity, sex, type of diabetes, duration of diabetes in 5 year categories, first 4 characters of post code). To be inclusive we will offer support for completion of questionnaires if remote online completion by the participant is not possible.

Nested Case control: This will be with written consent and include CRF visit, physical measures and data linkage to the clinical record for evidence of diabetes complications (current and future).

Case Cohort recruitment:

1. **From Diabetes Research Register:** We will utilise the NHS Research Scotland (NRS) Diabetes Research Network permission to contact research register of people with who have expressed a willingness to be involved in research. This register has a large cohort of people with diabetes (>14,000) who have given permission to be approached directly via email or letter or phone. People with diabetes in Scotland who are part of this system will be approached via email or letter or phone to take part. Remote participation does not require the R&D department permission of the Health Boards as no facility use is taking place. Within the data collected participants will be asked if they have had a positive COVID test or believe that they have had COVID infection.

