2. **From diabetes clinic lists or database search (SCI Diabetes):** To augment recruitment of COVID test positive participants we will also screen clinic lists and recruit directly. A member of the study team will screen diabetes clinic lists (eg trak or local clinical system, when possible SCI Diabetes) which routinely have a note of previous COVID infection. Name and CHI noted on screening log (excel spreadsheet held on NHS computer). If patient declines this is noted and no further action. If patient assents to contact then contact information taken (telephone and email – if neither possible postal address) and added to screening log. Electronic data collection link sent by preferred means. If electronic remote data collection not possible then paper questionnaires will be made available by post or study team will discuss over the phone. Cases identified to by SCI Diabetes search will be approached in writing with Caldicott Guardian approval in place within a Health Board (likely to be used in selected Health Boards only).
3. We will also advertise the study by leaflets and posters and via newsfeed to My Diabetes My Way, allowing self-referral to the study team.

NESTED CASE-CONTROL RECRUITMENT:

Cases, by definition, will have had a positive COVID test present on the clinical record. Potential cases will be selected from the cohort where a record of self-reported COVID infection is presented. Potential cases will be invited to CRF visit by telephone or email. Where assent is given by phone the clinical record will be checked to confirm positive COVID test, visit is arranged, and PIS sent. All other study procedures will take place only after face-to-face written consent is obtained at the CRF visit.

Controls will be selected from the pool of people who have completed the online questionnaire information and who have indicated that they have not had a **positive** COVID test and do not believe that they have had COVID infection. Those who had possible infection but subsequent test negative are included. Matching will be by age (5 year category),

ethnicity, sex, SIMD quintile and type of diabetes included in the participant completed questionnaire.

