5.4 INELIGIBLE AND NON-RECRUITED PARTICIPANTS

Participants who are not eligible will be informed and their details will be recorded on a screening log or within SCI Diabetes system. They will be thanked for their interest and no further data will be collected.

Ineligible participants may be removed from the dataset at the CI's discretion, if data and/or samples have been collected these will be removed/destroyed as applicable and this process will be documented.

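### In the nested case control study, late-found ineligibility can lead to discretionary, unmasked and irreversible removal of collected data, and the only example given may overlap with the symptoms being measured

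*Protocol*

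**What the plan says.** Section 5.3 opens with the nested study. Participants consent, their SCI Diabetes records are then checked, and a research nurse judges eligibility. It continues: "It may become clear at a later date that the participant is not eligible eg. has difficulty reading questionnaires or providing written answers". Support comes first: "Work arounds will be sought where possible (eg. verbally aid to support participation". Then: "However ineligible participants may have their data removed from the study, at the CI's discretion".

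Section 5.4 repeats the discretion and says that "if data and/or samples have been collected these will be removed/destroyed as applicable". It also says that the removal process is documented.

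Three other places matter:

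- Section 4.10 requires literacy in English. The criterion stands under the case cohort heading, and nested participants are drawn from that cohort (5.1).
- Section 4.5 says of the Wellcome questionnaire: "This is a comprehensive instrument covering physical, cognitive, and mental health domains".
- Section 7.2 makes the current 0-28 symptom score, case versus control, the primary analysis of the nested study.

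**The concern.** A rule that lets data leave a study is harmless if it is applied to facts fixed at entry, by someone who cannot see the results, and if the data stay available. This rule secures none of the three. No time limit is set. The decision is discretionary, in a study where staff know who is a case. The data and samples may be gone afterwards.

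The example sharpens the problem. Trouble with reading questionnaires or writing answers, noticed later, may be a literacy or language limit that was always there. It may also be a cognitive symptom, which is part of what the study measures. The protocol does not tell the two apart. If symptomatic people are removed more often in one group than in the other, the nested comparison is distorted. An analysis plan written later cannot repair this, because it cannot analyse what was destroyed.

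**Working it through.** **Inputs from the protocol (7.1).** 500 cases and 500 controls; 526 per group for 0.2 SD and 85 per group for 0.5 SD at 90% power, alpha 0.05; a detectable difference of 50% versus 40% with 500 per group.

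**Assumptions, not in the protocol.** Two-sided tests; 50% assigned to cases and 40% to controls; the share *d* of cases removed; the share *s* of those removed who are symptomatic; no controls removed unless stated.

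**The plan's own figures.** n per group = 2(1.960 + 1.2816)²/δ². For δ = 0.2 SD this is 2 × 10.507/0.04 = 525.4, so 526. For δ = 0.5 SD it is 2 × 10.507/0.25 = 84.1, so 85. Both reproduce. With 500 per group, 50% versus 40% has 89.0% power.

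**Selective removal, proportions.** Observed case prevalence = (250 − 500·d·s) / (500·(1 − d)). Power is against 500 controls at 40%.

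| Removed (d) | Symptomatic among removed (s) | Observed in cases | Contrast (points) | Power |
|---|---|---|---|---|
| 0% | – | 50.0% | 10.0 | 89.0% |
| 2% | 100% | 240/490 = 49.0% | 9.0 | 81.2% |
| 2% | 80% | 242/490 = 49.4% | 9.4 | 84.5% |
| 5% | 100% | 225/475 = 47.4% | 7.4 | 64.1% |
| 5% | 80% | 230/475 = 48.4% | 8.4 | 75.5% |
| 5% | 50% (unrelated) | 237.5/475 = 50.0% | 10.0 | 88.2% |

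**Selective removal, score.** The primary analysis uses a score. If the removed cases lie *m* SD above the mean of all cases, the remaining difference is 0.2 − d·m/(1 − d). For d = 5%:

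- m = 0.5: 0.2 − 0.026 = 0.174 SD
- m = 1: 0.2 − 0.053 = 0.147 SD
- m = 2: 0.2 − 0.105 = 0.095 SD

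**Does the direction have to be downward?** No. If 5% of controls were also removed, all symptomatic, controls would show (200 − 25)/475 = 36.8%. The contrast would be 47.4 − 36.8 = 10.5 points before rounding, close to the true 10. If only controls were removed in this way, it would rise to 50.0 − 36.8 = 13.2 points. Sign and size depend on who is removed, and the protocol gives no basis for that.

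**The case against.** The strongest defence is that the rule is milder than it looks. Section 5.3 seeks workarounds before removal. The example is not arbitrary, because it follows from a listed entry criterion. Removals leave a documented trail. The study matrix (4.4) already places the inclusion and exclusion assessment at week 0, and 5.2 puts written consent before any procedure. The illustration needs an assumed removal rate, and its first rows are a worst case. All of this stands. It lowers the weight of the point but does not remove it: workarounds are promised only where feasible, a record of a deletion does not bring data back, and nothing limits removal to a breach that existed at entry.

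A reader might infer three further faults that the protocol does not support.

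- *That removal contradicts the supported completion offered elsewhere.* Section 5.1 says: "To be inclusive we will offer support for completion of questionnaires if remote online completion by the participant is not possible". Section 5.3 takes the same approach, with support first and removal as a fallback, so there is no conflict.
- *That 5.1 and 5.3 disagree on when eligibility is settled.* In 5.1, for potential cases: "Where assent is given by phone the clinical record will be checked to confirm positive COVID test". That is a check of one fact before the visit. Section 5.3 describes a wider record check after consent. The two can follow one another.
- *That the cohort prevalence objective is biased.* Section 5.3 concerns the nested study, and 6.1 says that a completed questionnaire cannot be withdrawn because it is anonymous. The cohort result is largely outside this rule.

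**Conclusion.** The point holds for the nested case control study. Sections 5.3 and 5.4 create a power to remove data that is open in time, discretionary, not masked to group or results, and irreversible. Its only example does not separate an entry limit from a possible outcome. This is a rule of conduct fixed in the protocol, not a detail left to the analysis plan.

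It would go too far to say that people with cognitive long COVID will be selectively deleted, or that symptoms in cases will be understated. The protocol does not link the example to COVID, gives no removal rate, and does not confine removal to cases. Under the stated assumptions, 5% removal confined to cases costs between 0 and 2.6 percentage points of a 10-point contrast as the symptomatic share among those removed goes from 50% to 100%. The actual bias cannot be computed. This is a cheap improvement worth making, not a flaw that invalidates the design.

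**What to change.** In 5.3 and 5.4, replace discretionary removal with a fixed rule:

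1. Complete the week-0 eligibility check after written consent and before any study test, for cases and controls alike.
2. After that, exclude from analysis only for an objective breach of a listed entry criterion as it stood at entry, decided by a team member who has not seen the questionnaire and test results.
3. Flag and keep the data of excluded participants unless consent is withdrawn. Report exclusions by group with reasons, and run a sensitivity analysis that includes them.
4. Limit the reading and writing example to inability present at entry. Participants who develop or show difficulty later complete with support, and the mode of completion is recorded.

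The cost is a wording amendment to two sections and, at most, a record check done earlier on the visit day. The downside is that a few flagged or supported records stay in the data set.

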5.4 INELIGIBLE AND NON-RECRUITED PARTICIPANTS

Participants who are not eligible will be informed and their details will be recorded on a screening log or within SCI Diabetes system. They will be thanked for their interest and no further data will be collected.

Ineligible participants may be removed from the dataset at the CI's discretion, if data and/or samples have been collected these will be removed/destroyed as applicable and this process will be documented.

5.5 RANDOMISATION

Randomisation is not used in this study.

5.6 REPLACEMENT OF DROP OUTS

Controls may be replaced if a participant does not complete all the required tests necessary for the nested case control study.

6 DATA COLLECTION & MANAGEMENT

6.1 DATA COLLECTION

The study will utilise the excellent data resource we have within Scotland for individuals with diabetes. Study relevant data from SCI Diabetes will be transferred into a data management system. Previous trials have used this methodology and we will use this expertise in this study. We will draw on the extensive expertise and knowledge of the SCI-diabetes and Scottish hospital admission datasets as well as cognate studies of the effects of COVID in this population. We also include a formal interim analysis after approximately the first six months of data collection (50 cases and approximately 50 controls) to allow examination of various aspects of recruitment.

As noted we are expecting that COVID status will be included in the SCI Diabetes record. Research participation is recorded in SCI Diabetes.

If a participant completes a questionnaire but later wishes to be withdrawn this will not be possible as the data will be anonymous.

6.2 DATA MANAGEMENT SYSTEM

We will use the RedCap data management system (DMS) hosted on a secure server at The University of Glasgow. This system will host all study information with the exception of screening logs and secure link between patient identifiers and study ID - both of which will be held separately on NHS computers. The RedCap platform allows for direct data entry by participants using either personal computer or smartphone.

Data held in NHS – on secure computer in CRF at each recruiting site:

Screening log for invitation to cohort from clinic lists – this will include patient identifiers restricted to CHI, name, telephone number, email address, as well as study process details (date contacted, consent given to send link for questionnaire data).

After written consent a separate file will be maintained with CHI and study ID.

Data held in RedCap (University of Glasgow)

All Cohort study information. This is entered by the participant and includes:

1. Panel of limited demographics (age in 5 year categories, ethnicity, sex, type of diabetes, duration of diabetes in 5 year categories, first 4 characters of post code to allow calculation of SIMD quintile)
2. Contact details (telephone, email address) – optional for participant
3. Study questionnaires (Wellcome, DQOL, DDS-1, EQ5D)

For nested case control study to this will be added:

1. Nested case control screening information recording interest in study/ willingness to attend CRF

After written consent at CRF the following will be added:

2. study ID
3. completed data from CRF visit (incremental walking, hand grip, pulmonary function, waist and thigh measurement, bioimpedence)
4. Participant information including (age to nearest year, ethnicity, sex, type of diabetes, diabetes duration), **e-mail address and/or contact telephone number**
5. Self filled questionnaire
6. Electronic pseudonymised linkage to variables in electronic clinical record being

- a. Sci-diabetes with measures of glycaemia (HbA1c), nephropathy, retinopathy, foot disease
 - b. SMR01 with data on hospital admissions
 - c. Where possible COVID test data for positivity and cycle threshold (cT)
- 7.

The DMS will be based on the protocol and case report form for the study and individual requirements of the investigators. The case report form will collect only information that is required to meet the aims of the study and to ensure the eligibility and safety of the participant.

The database will be managed in line with all applicable principles of medical confidentiality and data laws. The Data Controller will be the University of Glasgow and the Data Custodian will be the CI.

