4.10 INCLUSION CRITERIA

Case cohort study (online questionnaires):

- Person with Diabetes (Type 1 or Type 2)
- Aged 18 or over
- Able to read and write in English

Nested case control study (CRF visits):

- Cases defined by positive COVID test in the clinical record. Cases will be invited sequentially from the cohort but will be selected to include at least 200 people in each of the diabetes subgroups (type 1 diabetes or type 2 diabetes).
- Controls defined by no positive COVID test in clinical records and no reported infection by participant. Controls will be matched after matching of a limited demographic panel available from the panel (age in 5 year bands, ethnicity, sex, type of diabetes, SIMD quintile).

All participants attending a research facility must have completed a COVID safety check before attending in person, in line with local guidance. Cases will be post-COVID and at least 10 weeks post positive test result.

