7.2 PROPOSED ANALYSES

An analysis plan will be prepared for the University of Glasgow Research Data Management department before the study closes, to detail what analysis will be performed on the data.

Case cohort study:

This includes **participant completed questionnaires only**. We will not have access to clinical record for whole group (limited to those in nested study) and will rely on patient self-report of COVID testing and infection to create groups. Analysis will be in three groups:

- a. Test positive COVID declared (**cohort A**)
- b. no test but self-declared COVID (**cohort B**)
- c. no COVID infection declared, including those with suspected infection but test negative (**control**)

Analysis of this data will include

1. **Frequency of COVID symptoms** (derived from question 1.3 Wellcome questionnaire: 28 domains answering yes/no for 0-28 score and by self-report at time of infection at 3 months and current (>3 months)).
 - a. **Primary analysis:** current score cohort vs control with adjustment for limited demographic panel: age band, ethnicity, sex, type of diabetes
 - b. Secondary analyses:
 - i. within cohort comparison of time of infection vs 3 months vs current
 - ii. comparison time of infection and 3 months vs current score of control (with adjustment)
2. **Other questionnaire data:** diabetes depression score, DQOL all of which are assessed currently only and will be assessed in cohort vs control.
3. Comparison of above end points in cohort B to cohort and controls.

NESTED CASE CONTROL STUDY

For this data, consent will allow access to confirm that patient is COVID test positive in the clinical record. Definitions and comparison will therefore be between:

Cases - COVID test positive in clinical record

Control - no previous clinical COVID infection reported by patient, no record positive COVID test.

Case vs control (First visit)

1. **Frequency of COVID symptoms** (derived from question 1.3 Wellcome questionnaire: 28 domains answering yes/no for 0-28 score and by self-report at time of infection at 3 months and current (>3 months)).
 - a. **Primary analysis:** current score case vs control with adjustment for age, sex, ethnicity, sex, type of diabetes, SIMD
 - b. Secondary analyses:
 - i. within cohort comparison of time of infection vs 3 months vs current
 - ii. comparison time of infection and 3 months vs current score of control (with adjustment)
 - iii. relationship of cycle threshold to symptom scores

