2. **Other questionnaire data:** diabetes depression score, DQOL all of which are assessed currently only and will be assessed in cohort vs control
3. **Walk test**
4. **Hand grip**
5. **Pulmonary function measures eg. FEV1**

Comparison of cases vs COVID positive cohort for demographics and main study measures.

Case vs control (First and second visit data)

1. **Frequency of COVID symptoms** (derived from question 1.3 Wellcome questionnaire: 28 domains answering yes/no for 0-28 score and by self-report at time of infection at 3 month, at time of first questionnaire, first visit and at second visit).
 - a. **Primary analysis:** second visit score case vs control (first visit) with adjustment for age, sex, ethnicity, sex, type of diabetes, SIMD
 - b. Secondary analyses:
 - i. within cohort comparison of time of infection vs all time points
 - ii. comparison time of infection and 3 months vs current score of control (with adjustment)
2. **Other questionnaire data:** diabetes depression score, DQOL all of which are assessed first and second visit cohort vs control (first visit)

3. **Walk test** first and second visit cohort vs control (first visit)
4. **Hand grip** first and second visit cohort vs control (first visit)
- Pulmonary function measures eg. FEV1** first and second visit cohort vs control (first visit)

B. Screening log. As above contain patient identifiers, will be held on NHS computers.

Output - acceptance rate for study

C. Study data - will be held within Redcaps platform. Outputs: process data on completion of the different modules of the study, final study dataset.

Key aspects will be

- a. Record of consent and electronic consent
- b. Ability to enter data to personal computer/ smartphone by participant
- c. Ability to enter separate data under same study ID for study visit
- d. Cloud exportable to SAS/ SPSS/ R

Analyses will be carried out by the study team using the statistical support offered by the University of Glasgow.

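### In the nested case-control study, the only SIMD source the protocol describes is a four-character postcode, so matching and symptom-score adjustment use an approximate deprivation quintile that record linkage could improve

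*Protocol*

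**What the plan says.** Location data in the online questionnaire are limited to part of a postcode. Protocol section 5.1 lists "duration of diabetes in 5 year categories, first 4 characters of post code" in the demographic panel, and section 6.2 gives its purpose: "first 4 characters of post code to allow calculation of SIMD quintile". Section 4.2 keeps name, address and CHI out of the cohort data.

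SIMD is a matching factor. Section 4.10 matches controls on "age in 5 year bands, ethnicity, sex, type of diabetes, SIMD quintile". Section 5.1 names the source, matching on age category plus "ethnicity, sex, SIMD quintile and type of diabetes included in the participant completed questionnaire". (Sections 1 and 4.9 give shorter matching lists without SIMD.)

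SIMD is also a covariate. In section 7.2 the nested primary analysis at the first visit is "current score case vs control with adjustment for age, sex, ethnicity, sex, type of diabetes, SIMD", and at the second visit "second visit score case vs control (first visit) with adjustment for age, sex, ethnicity, sex, type of diabetes, SIMD". The case-cohort primary analysis is "current score cohort vs control with adjustment for limited demographic panel: age band, ethnicity, sex, type of diabetes", with no SIMD term.

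Once a participant has consented in writing, section 6.2 refines age to the nearest year and lists linkage to glycaemia, complications, admissions and COVID test data. It names neither SIMD nor the full postcode. The same section says: "After written consent a separate file will be maintained with CHI and study ID".

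**The concern.** A truncated postcode can give only one value for everyone in its area. If neighbourhoods within that area differ in deprivation, a quintile taken from it is an area average or an arbitrary allocation. The protocol gives no rule for assigning it.

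Deprivation may plausibly be related both to COVID infection and to symptom burden. If matching and adjustment use the same coarse value, adjustment cannot recover what matching missed. Part of any case-control difference in symptom score could then reflect deprivation, even though the design appears to control for it twice. This is avoidable: section 4.4 already schedules an extract from the clinical record at the nested visits, and the identifier link is held by then.

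**Working it through.** **1. Trace the variable through the protocol.**

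| Use | Section | SIMD used? | Source named |
|---|---|---|---|
| Cohort primary analysis | 7.2 | No | – |
| Matching of nested controls | 4.10, 5.1 | Yes | Questionnaire, so four characters |
| Nested symptom score, first visit | 7.2 | Yes | None named |
| Nested symptom score, second visit | 7.2 | Yes | None named |
| Nested walk test, grip, lung function | 7.2 | No adjustment listed | – |

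For matching, the four-character source is explicit. For adjustment, it is the only source described anywhere.

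**2. The plan's own figures.** The protocol gives no figure for SIMD accuracy or for the size of a postcode area. Its nearest figures are the sample sizes in section 7.1. With n per group = 2(1.960 + 1.282)² / d², d = 0.2 gives 525.4, rounded up to 526, and d = 0.5 gives 84.1, rounded up to 85. Both reproduce, and neither bears on this point.

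**3. Illustrative simulation.** Every input here is an assumption.

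- There are 4,000 postcode areas with 20 small areas each. The small-area score is x = a + e, with a ~ N(0, ρ) shared within the postcode area and e ~ N(0, 1 − ρ). So ρ is the share of deprivation variance lying between postcode areas; it was varied from 0.2 to 0.9.
- The reference quintile is that of x. The proxy is the quintile of the postcode-area mean, ranked across areas.
- For residual confounding, the outcome equals the reference quintile, the log-odds of being a case rise by 0.3 per quintile, and there is no true case effect. The share left is the case-control difference adjusted for the five proxy categories, divided by the crude difference.

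| Between-area share ρ | Exact agreement | Two or more quintiles out | Confounding left after adjustment |
|---|---|---|---|
| 0.2 | 32% | 31% | 81% |
| 0.5 | 42% | 18% | 55% |
| 0.8 | 57% | 5% | 28% |
| 0.9 | 68% | 1% | 18% |

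With five equal groups, chance agreement is 1/5 = 20%. If the area mean is instead cut at the small-area quintile boundaries, agreement runs from 27% to 68% over the same range, so the unstated assignment rule also matters.

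**4. What this shows.** Within this model, agreement stays incomplete across the whole range, but its level depends almost entirely on ρ, which the document does not give.

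**The case against.** The strongest reply has four parts.

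- **The premise is external.** The protocol defines neither SIMD nor the area on which it is scored. This stands, so the conclusion is conditional.
- **The truncation is deliberate.** Broad demographics without identifiers support wide remote participation, and controls are chosen from the online pool before written consent. This stands for matching: the proxy is all that is available then, and no later derivation changes how pairs were formed.
- **The adjustment may not use the questionnaire value.** Section 7.2 says only SIMD. The linkage list in section 6.2 is not exhaustive, since section 4.5 plans blood pressure from SCI-Diabetes and section 6.2 does not list it. The analysis plan promised in section 7.2 could name another source. This stands in part: the four-character value is the only source described, not the only one possible. But an analysis plan can use a finer quintile only if the extract supplies it, and that is a data-collection decision belonging in the protocol.
- **The scope is narrow.** SIMD adjustment is specified only for the nested symptom score. This stands.

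A reader might infer that all matching and adjustment in the study will rest on a badly misclassified variable. The document does not support that. The cohort primary analysis makes no use of SIMD, linkage could yet supply a better covariate, and the simulated error runs from severe to moderate depending on an unknown input.

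**Conclusion.** The point holds for the nested case-control study. As described, SIMD quintile comes from four postcode characters, is a matching factor, and has no other described source for adjusting the two primary symptom-score analyses. If SIMD is scored on smaller areas than that, the quintile is approximate and some deprivation confounding remains.

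Its size is not known. The 32% to 68% agreement and the 81% to 18% of confounding left illustrate the assumed range of 0.2 to 0.9; they are not estimates for Scotland.

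A reader might want to turn this into bias on the outcome scale. Assuming deprivation confounds the score by 0.05 to 0.10 SD and 40% to 70% of that is left gives 0.4 × 0.05 = 0.02 SD to 0.7 × 0.10 = 0.07 SD. That is 10% to 35% of the 0.2 SD in section 7.1, or about 0.3 to 1.1 times the standard error of √(2/500) = 0.063 SD. Both inputs are assumed and the document supports neither, so this range should not be quoted as the study's bias.

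The cohort primary analysis is not affected. For walk test, grip and lung function, only the matching is affected.

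**What to change.** For nested participants, after written consent, derive SIMD quintile inside the NHS from the full postcode in the clinical record, using the CHI–study ID file. Pass only the quintile to RedCap and add it to the linked variables in section 6.2. In section 7.2, name it as the SIMD covariate for the nested analyses, and report how well case-control pairs agree on it.

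Keep the four-character value for pre-consent matching only. State how a quintile is assigned from it and describe it as an area-level proxy.

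The cost is one derived field in an extract already scheduled in section 4.4, plus wording and the amendment approvals that section 12.1 requires. No extra participant contact is needed, and no full postcode leaves the NHS. The downside is that some pairs matched on the proxy will differ on the finer quintile and rely on adjustment. The change improves adjustment, not matching, and should be made before the linkage specification is final.
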